11.1. Data Collection

To ensure data quality and completeness, all required data will be recorded on case report forms (CRFs) provided by the sponsor. Data will be entered onto electronic case report forms by the investigational site or designee. Case Report Forms should be completed accurately during and in a timely manner after any visit in the study. The Principal Investigator or appointed designee must review the case report forms and sign them, certifying their accuracy. Completed case report forms should be submitted to the sponsor within two weeks of completion of a study visit.

Each patient will be followed for a period of 12 months after implant according to the schedule and standard practice at the enrolling centers. There will be no additional procedures, for subjects who participate in the study. Subjects are expected to be followed at implant, then at First Follow-up ($30 \sim 100$ days), and 12-Month Follow-up (365 ± 30 days) post-implant. An intermediate visit may be scheduled in a number of patients, per physician discretion.

For subjects who are not scheduled to visit the clinic for a follow-up, a subject contact (e.g. phone call) will ensure capture of the endpoint related information, however it is strongly recommended to perform an in-office visit for at least the First Follow-up visit.

Table 3 provides an overview of the data to be collected at each visit.

				Follow Up	
Data Collected	Enrollment	Implant	First (30 ~ 100 days) Office	12-Month (365 ± 30 days) Office/Phone	Additional Office/Phone
Informed Consent	Х				
Inclusion/Exclusion	Х				
Demographic data	Х				
Medical History	Х				
LAA imaging (TEE/CT/MRI)	X ^{a,b}	Xa	Х	Xa	X ^a
Medication Regimen	Х	Х	Х	Х	Х
Current status and Vital Signs	Х	Х	Х	Х	Х
Adverse Event and Device Deficiency Reporting	X	X	X	X	Х

Table 3: Data Collection Overview

^a collected only if performed

^b within 3 calendar days prior to implant

11.2. Informed Consent

In order to determine eligibility of a subject, the investigator needs to implement the consent process and verify and document the subject meets the inclusion/exclusion criteria. Informed consent is required from all patients (or their legal representatives) prior to the patient's participation in the study. The patient should be given ample time to consider participation and ask questions if necessary. An approved informed consent form shall be signed and personally dated by the subject (or legal representative). The original, signed document is to be kept with the subject's file and a copy must be provided to the subject.

11.3. Enrollment Visit

Only those subjects who provide consent and meet all of the study enrolment criteria may be enrolled and will have baseline data collected. Subjects who provide informed consent but do not meet all of the study enrolment criteria will be considered Consent Ineligible.

The data collection at Enrollment Visit includes:

- Demographic data, including: age at time of consent, gender, and ethnic;
- Risk factors, including those used to calculate HAS-BLED, CHADS₂ and CHA₂DS₂-VASc scores;
- Medical and cardiac history, including: cardiovascular diseases; prior history of ischemic stroke, hemorrhagic stroke or TIA; previous cardiac procedures; history of bleeding; indication for LAA occlusion;

Form/Template 92120219_Rev/Ver G Confidential WATCHMAN FLX HK Protocol, 92427834, Rev/Ver D Page 26 of 51

- Current medical status; vital signs; AF status (paroxysmal, persistent, permanent);
- Current medication regimen for the use of antiplatelet and anticoagulation medications;
- Adverse Events and Device Deficiency, if applicable.

11.4. LAA Imaging (e.g. TEE/CT/MRI)

Prior to implantation with the WATCHMAN FLX device, an Enrollment TEE (or alternative imaging method) is a clinical standard to confirm there is no thrombus in the LAA or left atrium. If an intracardiac thrombus is visualized by echocardiographic imaging, the patients will not be implanted. Re-assessment may be scheduled per physician's discretion.

The Implant LAA imaging will also allow the investigator to obtain proper measurements of the LAA to correctly size the device, confirm device release criteria are met prior to device release, and to confirm adverse events have not occurred during the implant procedure (i.e., pericardial effusion). If an intracardiac thrombus is visualized by echocardiographic imaging, the patients will not be implanted. Re-assessment may be scheduled per physician's discretion.

The Follow-up LAA imaging is a clinical standard after the WATCHMAN FLX procedure, it is conducted to assess flow through and around the WATCHMAN FLX device, to ensure sealing and to verify there is no thrombus on the surface of the device prior to stopping dual platelet inhibition or warfarin. Additional LAA imaging may be conducted at the discretion of the investigator and according to center's practice.

Certain information from TEE/CT/MRI conducted during the course of the study will be captured on the study case report forms, including: heart rhythm; valve status; pericardial status; atrial septum characteristics; LAA size and type of anatomy; thrombus assessment.

For measurement of per-device flow:

- Use multiple TEE views (0°, 45°, 90°, and 135°) or 3D-TEE
- Echo colour Doppler TEE: set Nyquist limit to detect low velocity flow (20–30 cm/s). If leak is present, measure only the mosaic (high-velocity) colour of a communicating flow in multiple projections
- Use same settings during implantation and follow-up
- Document largest measurement as size of leak and achieved angle of measurement by TEE or CT/MRI

11.5. *Implant Procedure*

The implant procedure should be performed using standard of care methods established by the investigational center (e.g. sterile technique, personnel requirements, etc.). Implantation of the WATCHMAN FLX LAA Closure Device should only be performed by physicians trained in percutaneous and transseptal procedures who have completed the WATCHMAN FLX training program. Refer to the WATCHMAN FLX LAA Closure Technology Directions for Use for detailed instructions regarding the implantation and use of the WATCHMAN FLX technology. The following will be assessed during implant procedure and documented on case report forms for enrolled subjects:

- WATCHMAN FLX Device and Access System usage information, including device size and compression post-implant, procedure time (from first sheath inserted to last sheath removed);
- LAA imaging (as described in section 11.4): LAA measurements; intracardiac thrombus, device position, LAA seal, thrombus on the device surface;
- Concomitant procedures;
- Current medical status; vital signs; AF status;
- Current medication regimen for the use of antiplatelet and anticoagulation medications;
- Serious adverse events, adverse events and device deficiencies during implant procedure. Data to be collected for peri-procedural complications include, but are not limited to:
 - Cardiovascular events: pericardial effusion, cardiac tamponade, bleeding, stroke (ischemic/non-ischemic), TIA, systemic embolism (please refer to Appendix A for definitions of stroke/TIA and classification of bleeding events)
 - ICU: Length of stay
 - Conventional care unit: Length of stay
 - Device/procedure related complications

11.6. Follow-up Procedures

Subjects are expected to be followed at First $(30 \sim 100 \text{ days})$ and 12-Month post-implant or until the study is terminated. An intermediate visit may be scheduled in a number of patients, per physician discretion. For subjects who are not scheduled to visit the clinic for a follow-up, a subject contact (e.g. phone call) will ensure capture of the endpoint related information, however it is recommended to perform an office visit for at least the First Follow-up visit.

i) In-Hospital Visit

The following will be assessed during each in-hospital visit and documented on case report forms for enrolled subjects:

- Current medication regimen for the use of antiplatelet and anticoagulation medications;
- Procedures performed since last visit;
- Current medical status; vital signs; AF status;
- LAA imaging (as described in section 11.4): device position, LAA seal, thrombus on the device surface, intracardiac thrombus and residual atrial septal shunt;
- Serious adverse events, adverse events and device deficiencies experienced since last visit. Data to be collected include, but are not limited to (please refer to Appendix A for definitions of stroke/TIA and classification of bleeding events):
 - ER admission due to WATCHMAN FLX implant related clinical events (stroke/TIA (ischemic/non-ischemic), systemic embolism, major and minor bleeding)

- Hospitalization (ICU and Ward) due to WATCHMAN FLX implant related clinical events (stroke/TIA (ischemic/non-ischemic), systemic embolism, major and minor bleeding)
- Specialist visits due to WATCHMAN FLX implant related clinical events (stroke/TIA (ischemic/non-ischemic), systemic embolism, major and minor bleeding)
- Diagnostic procedure following a clinical event related to WATCHMAN FLX (stroke/TIA (ischemic/non-ischemic), systemic embolism, major and minor bleeding)

ii) Subject Contact

For subjects who are not scheduled to visit the clinic for a follow-up, a subject contact (e.g. phone call) will ensure capture of the endpoint related information. The following will be assessed during each subject contact and documented on case report forms for enrolled subjects:

- Current medication regimen for the use of antiplatelet and anticoagulation medications
- Serious adverse events, adverse events and device deficiencies experienced since last visit. Data to be collected include, but are not limited to (please refer to Appendix A for definitions of stroke/TIA and classification of bleeding events):
 - ER admission due to WATCHMAN FLX implant related clinical events (stroke/TIA (ischemic/non-ischemic), systemic embolism, major and minor bleeding)
 - Hospitalization (ICU and Ward) due to WATCHMAN FLX implant related clinical events (stroke/TIA (ischemic/non-ischemic), systemic embolism, major and minor bleeding)
 - Specialist visits due to WATCHMAN FLX implant related clinical events (stroke/TIA (ischemic/non-ischemic), systemic embolism, major and minor bleeding)
 - Diagnostic procedure following a clinical event related to WATCHMAN FLX (stroke/TIA (ischemic/non-ischemic), systemic embolism, major and minor bleeding)

11.7. Study Completion

Each subject will be followed for 12 months after the implant. In case of premature termination of the study, data collection will stop accordingly. As this is an observational study, subjects will be managed according to standard of care as per centers practice following termination/completion of the study.

11.8. Source Documents

Printed, optical or electronic document containing source data shall be used; examples include hospital records, laboratory notes, device accountability records, radiographs, records kept at the investigation site, and at the laboratories involved in the clinical study.

Form/Template 92120219_Rev/Ver G Confidential WATCHMAN FLX HK Protocol, 92427834, Rev/Ver D Page 29 of 51 Where copies of the original source document as well as printouts of original electronic source documents are retained, these shall be signed and dated by a member of the investigation center

12. Statistical Considerations

An overview of the study design, sample size and statistical analysis is provided below.

team with a statement that it is a true reproduction of the original source document.

12.1. Sample Size Justification

This is a prospective, non-randomized, multi-center observational study with no formal prespecified hypothesis test. All subjects will be followed for up to 12 months or until the study is terminated.

A sample size of up to 50 subjects was chosen to observe the safety and effectiveness of the WATCHMAN FLXTM Left Atrial Appendage Closure (LAAC) Device for subjects with non-valvular atrial fibrillation to reduce the risk of stroke in Hong Kong area.

The ongoing PINNACLE FLX study is designed to establish the safety and effectiveness of the WATCHMAN FLXTM Left Atrial Appendage Closure (LAAC) Device for subjects with non-valvular atrial fibrillation. The study has enrolled 398 subjects, and each subject will be followed for 2 years. However, the PINNACLE FLX study is conducted exclusively in the U.S. Although it is assumed that ethnic difference might not play an important role in the performance of the left atrial appendage closure, a small sample size study in Hong Kong should be able to provide valuable information supporting this assumption.

12.2. Statistical Analysis and Data Sets

There is no hypotheses testing in this small sample size observational study.

The Primary Effectiveness Endpoint is the occurrence of non-effective LAA closure defined as any peri-device flow > 5mm demonstrated by TEE/CT/MRI at First Follow-up.

The Primary Safety Endpoint is the occurrence of one of the following events between the time of implant and within 7 days following the procedure or by hospital discharge, whichever is later: all-cause death, ischemic stroke, systemic embolism, or device- or procedure-related events requiring open cardiac surgery or major endovascular intervention such as pseudoaneurysm repair, AV fistula repair, or other major endovascular repair. Percutaneous catheter drainage of pericardial effusions, snaring of an embolized device, thrombin injection to treat femoral pseudoaneurysm and nonsurgical treatments of access site complications are excluded from this endpoint.

Roll-in subjects are excluded from all Primary Endpoint analyses, and will be treated separately analysis set for the Primary Effectiveness analysis includes implanted subjects with a completed First Follow-up visit. The analysis set for the Primary Safety analyses will be the "intent-to-treat" analysis set, including implanted or attempted subjects. It is estimated that both Primary Effectiveness analysis and Primary Safety analysis dataset will include at least 40 subjects.

For the Primary Effectiveness Endpoint, it might be considered reasonable if up to 3 primary effectiveness endpoint events should occur in this small sample size study.

For the Primary Safety Endpoint, it might be considered reasonable if up to 3 primary safety endpoint events should occur in this small sample size study.

Missing data will not be dealt with systematically in this small sample size study. A tippingpoint analysis might be conducted for the Primary Effectiveness Endpoint to assess the impact of different assumptions about the missing data on interpretation of the results.

For Secondary Endpoint and additional analysis, different data sets could be used exploratively.

While no formal hypothesis tests will be performed, descriptive statistics will be generated for the data collected at enrollment, during the implant procedure and at follow-up. For continuous variables, the mean, standard deviation, median, range and 95% confidence intervals will be reported. Confidence intervals (95%) for the difference between means will be used to compare groups. For proportions, 95% confidence intervals will be reported. For time-to-event analyses, all subjects not having an event or lost to follow-up will be censored at the time of the last documented follow-up visit.

For a sample size of 50, the 95% CIs of the rates for 0~5 events are as follows (exact methods), Table 4:

Events	Rates (n=50)	Lower 95% CI	Upper 95% CI
0	0%	0.0%	7.1%
1	2%	0.1%	10.6%
2	4%	0.5%	13.7%
3	6%	1.3%	16.5%
4	8%	2.2%	19.2%
5	10%	3.3%	21.8%

Table 4: 95% confidence interval for 0~5 events

Although not powered in the small sample study, explorative analyses may include, but will not be limited to the study endpoints. A variety of methods may be utilized in order to assess associations between the likelihood of each of the study endpoints and the patient and procedural characteristics outlined below. Covariates will be chosen for inclusion in the models based on the number of patients with complete data for each outcome according to the prioritization in Table 5.

Methods to model multivariate associations may include but are not limited to the following:

1) Univariate analysis of individual predictors, and subsequent construction of multivariate logistic regression models incorporating all significant univariate predictors.

Page 31 of 51

- 2) Parsimonious multivariate logistic regression models constructed through stepwise selection algorithm.
- 3) Classification and regression tree models.

Table 5: Covariates of Interest

1. Age ≥ 80 years
2. Gender
3. Type of AF (paroxysmal; persistent; permanent)
4. Previous Stroke/TIA
5. Previous major bleeding event
6. HASBLED \geq 3
7. $CHADS_2 \ge 3$
8. CHA_2DS_2 -VASc ≥ 5
9. Type of anticoagulation therapy (Warfarin; NOACs; antiplatelet)
10. Multiple concomitant procedures vs watchman implant only

13. Data Management

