The first iteration of the WATCHMAN FLX Device began a limited market release (LMR) in Europe in 2015 and was implanted in 213 patients. The rate of embolization (3.8%) for this initial FLX iteration was greater than anticipated. Boston Scientific elected to make design enhancements to the device. These design enhancements were incorporated into the current WATCHMAN FLX Device. The PINNACLE FLX study is designed to establish the safety and effectiveness of the WATCHMAN FLXTM Left Atrial Appendage Closure (LAAC) Device for subjects with non-valvular atrial fibrillation. The study completed the enrollment of 398 subjects on November 9, 2018. Each subject will be followed for 2 years. However, the PINNACLE FLX study is conducted exclusively in the U.S. Although it is assumed that ethnic difference might not play an important role in the performance of the left atrial appendage closure, we designed this HK FLX study to observe the safety and effectiveness of the WATCHMAN FLXTM LAAC Device for subjects with non-valvular atrial fibrillation to reduce the risk of stroke in Hong Kong area.

5. Device Description

5.1. *Product Description*

The WATCHMAN FLX Delivery System consists of the Delivery Catheter and the pre-loaded Closure Device, **Figure 1**. The WATCHMAN FLX Delivery System is used in conjunction with a WATCHMAN Access System. Together, the WATCHMAN Access System and WATCHMAN FLX Delivery System permit device placement in the LAA via femoral venous access and crossing the inter-atrial septum into the left atrium. The WATCHMAN Access System is commercially-available and a required accessory for use with the WATCHMAN FLX procedures.

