7.1. Primary Effectiveness Endpoint

The occurrence of non-effective LAA closure defined as any peri-device flow > 5mm demonstrated by TEE/CT/MRI at First Follow-up.

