7.2. Primary Safety Endpoint

The occurrence of one of the following events between the time of implant and within 7 days following the procedure or by hospital discharge, whichever is later: all-cause death, ischemic stroke, systemic embolism, or device or procedure related events requiring open cardiac surgery or major endovascular intervention such as pseudoaneurysm repair, AV fistula repair, or other major endovascular repair.

NOTE: Percutaneous catheter drainage of pericardial effusions, snaring of an embolized device, thrombin injection to treat femoral pseudoaneurysm and nonsurgical treatments of access site complications will be captured as adverse events (AEs), and are excluded from this endpoint.

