A subject who signs informed consent, meets eligibility criteria and has had the WATCHMAN FLX Access Sheath inserted to implant the device, but eventually does not receive a WATCHMAN FLX device will be classified as "**Attempt**". These subjects may be withdrawn, unless a re-implant of a study device is planned, per physician discretion. If subjects are re-assessed for WATCHMAN FLX implant, as per physicians' discretion, then a reconsent must be obtained for participating in the registry. These subjects will be handled as "Implant" (see next section), if the re-implant is successful. Subjects who eventually have not received a WATCHMAN FLX device at the time of enrollment closure will remain classified as "Attempt" and be withdrawn. There are no FU requirements for Attempt subjects; however, adverse events will be collected up to the point of subject withdrawal. Attempt subjects count towards the enrollment ceiling and will be used for analyses of the endpoints. The original signed Informed Consent must be maintained in the center's study file and the following forms must be completed:

- eCRFs in the "Baseline" and "Implant" folders
- "Adverse Event" forms for any adverse event that occurs after signing the Informed Consent, up to the point of subject withdrawal.
- "Patient Status" form for withdrawal, when applicable.

The date at which the patient status form has been completed will be the point of subject withdrawal.

Implant

A subject who is successfully implanted with the WATCHMAN FLX device will be classified as "**Implant**". These subjects are followed in accordance with the FU schedule and included in all study analyses. All applicable case report forms per the protocol must be completed. The original signed Informed Consent and any relevant documentation must be maintained in the center's patient file.

Roll-in and non-roll-in

Each site might have up to 2 roll-in subjects if the site has never implanted a WATCHMAN FLX before. Roll-in subjects should be decided before the implant procedure, and might be classified as **Attempt** or **Implant** after the procedure. Roll-in subjects are enrolled and counted to the ceiling of the sample size. Other enrolled subjects are defined as non-roll-in.

Figure 2: Subject Status and Data Collection Flow Chart

11. Study Methods

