4 GENERAL STATISTICAL METHODS

4.1 Analysis Sets

Roll-in subjects are excluded from all primary and secondary endpoints analyses and will be treated separately.

The primary analysis set for the primary effectiveness analysis will be the "per-protocol" analysis set, including implanted subjects with a completed first follow-up visit. The primary analysis set for the primary safety analysis will be the "intent-to-treat" analysis set, including implanted or attempted subjects. It is estimated that both primary effectiveness analysis and primary safety analysis dataset will include at least 40 subjects. For secondary endpoint and additional analysis, different datasets could be used exploratively.

The definitions on the different subject status and classification are provided as below:

Consent Ineligible: A subject who has signed informed consent but is found to not meet eligibility criteria will be classified as "**Consent Ineligible**". There are no FU or adverse event reporting requirements for consent ineligible subjects. Subjects determined to be Consent Ineligible do not count towards the enrollment ceiling and will not be used for analysis of the endpoints.

Intent: A subject who signs informed consent, meets eligibility criteria, but then does not undergo an implant of a WATCHMAN FLX device will be classified as "**Intent**". There are no FU or adverse event reporting or primary endpoint analysis requirements for Intent subjects. Intent subjects do not count towards the enrollment ceiling and will not be used for analysis of the endpoints.

Attempt: A subject who signs informed consent, meets eligibility criteria and has had the WATCHMAN FLX Access Sheath inserted to implant the device, but eventually does not receive a WATCHMAN FLX device will be classified as "**Attempt**". There are no FU requirements for Attempt subjects; however, adverse events will be collected up to the point of subject withdrawal. Attempt subjects count towards the enrollment ceiling and will be used for analyses of the endpoints.

Implant: A subject who is successfully implanted with the WATCHMAN FLX device will be classified as "**Implant**". These subjects are followed in accordance with the FU schedule and included in all study analyses.

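### Primary effectiveness has no way to count an embolised, removed or never-placed device as non-effective closure, and primary safety covers only part of that gap

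*Protocol*

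**What the plan says.** **Effectiveness.** Protocol 7.1 defines the event as "The occurrence of non-effective LAA closure defined as any peri-device flow > 5mm demonstrated by TEE/CT/MRI at First Follow-up", and SAP 3.1 repeats it. Protocol 12.2 says the "analysis set for the Primary Effectiveness analysis includes implanted subjects with a completed First Follow-up visit". SAP 4.1 calls this set per-protocol, "including implanted subjects with a completed first follow-up visit". Roll-in subjects are excluded.

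**Attempt subjects.** Protocol 10.3 says "Attempt subjects count towards the enrollment ceiling and will be used for analyses of the endpoints", and SAP 4.1 carries the same sentence. Protocol 10.3 also says "There are no FU requirements for Attempt subjects; however, adverse events will be collected up to the point of subject withdrawal". Only the safety set is described as the intent-to-treat "analysis set, including implanted or attempted subjects" (Protocol 12.2).

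**Safety.** Protocol 7.2 counts all-cause death, ischemic stroke, systemic embolism, and device- or procedure-related events that need open cardiac surgery or major endovascular intervention. The window closes at 7 days or discharge, whichever is later. It excludes, among other things, "snaring of an embolized device", which is kept as an adverse event. SAP 3.5 lists device embolization among the additional and other major clinical events in both reports, and SAP 5.5 reports patient and device dispositions.

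**Missing data.** SAP 7.5 first says missing data will not be handled systematically. It then treats dropouts and withdrawals as missing at random with multiple imputation, and treats missing follow-up data as not at random but imputed by the same techniques. A tipping-point analysis is optional.

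**Yardstick.** Protocol 12.2 says up to 3 events on each primary endpoint might be considered reasonable, and expects at least 40 subjects in each set.

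**The concern.** The endpoint is named for failure of closure but measures only leak around a device that is present. An appendage left open because the device has gone, or was never placed, is the plainest failure of closure, and the definition has no place for it. The reported rate is therefore conditional on the device having been placed and having stayed in place.

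The alternative treatments of such a subject are exclusion, scoring as a non-event, or imputation from subjects with a device. Each gives a lower non-effective closure rate than counting the failure, so the error can only favour the device. Protocol 6 and SAP 2 say the data may be used for product registration in other areas, so the headline figure may be read without the descriptive tables that qualify it.

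The Attempt wording is a separate, internal contradiction. One rule uses these subjects for the endpoints; the other leaves them out of one of the two primary endpoints.

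**Working it through.** **1. The plan's own figures.** Exact (Clopper-Pearson) limits are the 2.5% quantile of Beta(x, n−x+1) and the 97.5% quantile of Beta(x+1, n−x). With n = 50 they reproduce all six rows of Protocol Table 4; for example, 3/50 = 6% (1.3% to 16.5%). The figure of at least 40 agrees with 50 − 5 sites × 2 roll-ins = 40. At that maximum, the effectiveness set has no room for a single Attempt subject or missed visit.

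**2. Subjects traced through the rules.**

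| Subject | Primary effectiveness | Primary safety |
|---|---|---|
| No device can be placed (Attempt) | Outside the set | Event only if something else qualifies |
| Device embolises during the procedure, is snared, no other is placed (Attempt) | Outside the set | Event only if something else qualifies |
| Implanted; embolises inside the window, snared, not re-closed | No rule: non-event or missing | Event only if something else qualifies |
| Implanted; embolises inside the window and needs open cardiac surgery or major endovascular intervention, or leads to death, ischemic stroke or systemic embolism | Never an event: non-event, missing, or outside the set | **Event** |
| Implanted; embolises after the window | No rule: non-event or missing | Not an event, because the window has closed |

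**3. Whether imputation closes the gap.** Suppose 38 subjects have imaging and 2 have leaks, and two lost-device subjects are imputed at the observed rate. Expected events are 2 + 2 × (2/38) = 2.11, and 2.11/40 = 5.3%. Each open appendage is given about a 5% chance of being a failure.

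**4. How many such subjects to expect in 40 (illustrative).** Protocol 4.2 gives no rate for the current device.
- Non-implantation at earlier-device rates: EWOLUTION 98.5% deployed, 40 × 0.015 = 0.6; ASAP 94.0% placed, 40 × 0.06 = 2.4.
- Embolisation: the only FLX figure is in "The rate of embolization (3.8%) for this initial FLX iteration was greater than anticipated", and the device was then redesigned. I take 3.8% as the top of an assumed range starting at 0.5%. The chance of at least one is 1 − (1 − p)^40:
  - p = 0.5%: 18%
  - p = 2%: 55%
  - p = 3.8%: 79% (expected number 40 × 0.038 = 1.52)

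These are chances of any embolisation. The documents do not say what share is snared, occurs late, or is successfully re-closed, so the chance of a hidden failure is lower by an unknown amount.

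**5. Effect on the result.** Take 40 non-roll-in subjects with 2 leaks and 2 unclosed appendages.

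| Handling of the 2 unclosed | Rate | Exact 95% CI |
|---|---|---|
| Dropped from the set | 2/38 = 5.3% | 0.6% to 17.7% |
| Kept as non-events | 2/40 = 5.0% | 0.6% to 16.9% |
| Counted as failures | 4/40 = 10.0% | 2.8% to 23.7% |

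The first two lie within the 3-event yardstick; the third does not.

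**The case against.** The best defence is that this is a disclosed design choice. SAP 4.1 labels the effectiveness set per-protocol. Attempt subjects are in the safety set. Snaring is captured as an adverse event, embolisation is tabulated in both reports, and dispositions are reported. There is no hypothesis test, so no error rate or power is affected, and the 3-event yardstick is soft: passing it triggers nothing. The stated objective is to observe safety and effectiveness in reducing stroke risk, and ischemic stroke or systemic embolism is a separate 12-month endpoint. All of this stands. It argues against replacing the primary endpoint, but descriptive listing does not correct the headline rate or its interval, and it neither supplies a rule for a lost device nor resolves the Attempt contradiction.

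A reader might also infer more than the documents support:
- *That embolisation counts in neither primary endpoint.* Not so: an embolisation inside the window with surgical, major endovascular, death, ischemic stroke or systemic embolism consequences is a primary safety event.
- *That the snaring exclusion hides every snared case.* For an embolisation at, say, day 20 after discharge, the closed window is the reason, and even open surgery would not count.
- *That a lost-device subject is certainly scored as a non-event.* The plan is silent; missing is an equally available reading.
- *That 3.8% describes the study device.* It belongs to the iteration before the redesign. The non-implant rates likewise come from an earlier device, and Protocol 5.1.1 says FLX adds redeployment after full recapture.

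**Conclusion.** The point holds in a limited form. As defined, primary effectiveness cannot record an embolised, removed or never-placed device as non-effective closure; no rule scores an implanted subject whose device is gone; and imputation as planned would assign such a subject the leak risk of subjects whose device stayed in place. A snared embolisation without another qualifying event, and any embolisation after the safety window, falls outside both primary endpoints. The Attempt sentence contradicts the implanted-only effectiveness set.

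The size is uncertain. With the assumptions above, 0.6 to 2.4 of 40 subjects would end without a device, and the chance of at least one embolisation is 18% to 79%, not all of them hidden failures. The shift from about 5% to 10% rests on an invented but plausible case of 2 leaks and 2 unclosed appendages. What is affected is the point estimate, its interval and its reading against the yardstick. The documents do not support a claim that the primary endpoint is invalid or has to be replaced.

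**What to change.** 1. Keep peri-device flow above 5 mm as the primary criterion. In Protocol 12.2 and SAP 3.1, 4.1 and 7.5, state that an implanted subject whose device has embolised or been removed without re-closure by First Follow-up is scored as non-effective closure, not as a non-event and not imputed as missing at random.
2. Pre-specify one supplementary closure-failure rate with an exact 95% CI over all implanted or attempted non-roll-in subjects, counting attempts that end without a device as failures. State how subjects with a device but no First Follow-up imaging enter it. Report it beside the flow-only rate and the 3-event yardstick.
3. Reconcile the Attempt sentence in Protocol 10.3 and SAP 4.1 with the implanted-only effectiveness set, for example by naming the endpoints in which Attempt subjects are used.

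**Cost.** A protocol and SAP amendment, with whatever approvals Protocol 14 requires, one extra table row, and a possibly less favourable figure. No new data are needed: the Implant and Adverse Event forms for Attempt subjects (Protocol 10.3), device usage at implant (Protocol 11.5) and dispositions (SAP 5.5) are already collected.
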